On Day 1 (first treatment) and 15 (excisional biopsy), all patients will have blood (4 vials) and urine (25-50 ml) samples taken. Local reactions to injections will be monitored for non-specific signs such as bleeding, arythema, infection, or irritation. We don't anticipate specific changes in the pigmented lesion related to the injection in this short time period, however all changes will be noted.

On Day 15, following the second intralesional injection an excisional biopsy will be performed following standard surgical techniques, as follows: ellipse of skin encompassing the pigmented lesion extending into the subcutaneous fat will be performed to achieve a grossly clear but narrow margin of excision. This small defect will be closed primarily with interrupted sutures. The biopsied specimen will be subsequently evaluated using standard histological techniques to confirm diagnoses, assess margin status (clear or involved) and depth of lesion invasion. The depth of lesion invasion will dictate the extent of subsequent surgical excisions and margin selection according to standard National Comprehensive Cancer Network (NCCN) guidelines. Pre-biopsy intralesional injections of 0.1ml into the lesion will not alter dimensions or architecture of the lesion or impact the extent the subsequent biopsy required. Lesions that are felt to be too large for closure without tissue manipulation or creation of flaps, will be biopsied using a punch biopsy sampling technique whereby 4mm diameter discs of tissue from representative areas of the lesion will be taken to confirm the diagnosis and the depth of invasion. The depth of invasion will dictate the extent and complexity of subsequent surgery required to remove the lesion and achieve clear margins according to NCCN guidelines. The biopsied specimen will be processed as follows: using a 22G needle a fine needle aspiration biopsy will be performed (the needle will be passed through the center of the lesion two times) for RNA analysis. The remainder of the tissue will be sent to pathology for standard histological assessment. The pathologist will also report the extent of observed tumor infiltrating lymphocytes (TILs) associated with treatment compared to control injections. Blood and urine will be assessed using metabalomic and proteomic methods to assess systemic immune response to treatment.

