		Day 8 Clinical Visit -IL-2 treatment administered			Day 8 Clinical Visit -Nothing collected for sub-study at this visit
		Day 15 Clinical Visit -Area of skin suspected of cancer photographed -Blood sampled – 4 tablespoons (60 ml) -Urine Sampled – 3 to 4 tablespoons (50 ml)			Day 15 Clinical Visit -Blood sample – To be used in proteomic sub- study (study of protein levels found in blood) -Urine Sample – To be used in metabolomic sub- study (study of metabolites released in urine)
Standard of Care		-Surgical excision			-Biopsy sample collected from tissue removed during excision – To be used in RNA analysis sub- study (study of genes that may be involved in cancer development and growth)
Standa		-Confirmed melanoma patients Follow up every 6 months for 5 years			

Figure 2 Clinical and Sub-study Procedures

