#### Analysis of Data

#### Outcome measure/study objectives:

Assessment of Number of Patients Needed to Obtain Significance [**Time Frame: 1 year**] – Data will be analyzed in order to achieve a statistically significant differentiation between treatment and control outcomes in study measures including tumor infiltrating lymphocytes (TILs) and circulating immunomodulators.

Assessment of Metastasis [**Time Frame: 5 years**] - All patients will receive assessments every 4 months for 2 years and then biannual assessments for years 3-5 after the initial intervention to assess disease metastasis in treatment and control groups. Both number of new metastases (integer value) and thickness (mm) will be measured as a part of this assessment.

Sub-Study Outcome Measure:

Assessment of RNA genetic profile **[Time Frame: 5 years]** - RNA analysis of excised tissue will be compared to unaffected patient tissue obtained from the clear margins of the excisional biopsy to assess genetic changes resulting from the melanoma and treatment/placebo injections. RNA analysis will occur at [name] laboratory (Sir Charles Tupper Medical Building, 11F11) at Dalhousie University.

Assessment of Systemic Immune Response: Proteomic Analysis [**Time Frame: 5 years**] - Proteomic analysis will be conducted on blood samples to assess systemic immune response to both treatment and control groups. Serum collected from patient blood samples will be used for proteomic analysis to assess protein expression, including circulating immunomodulators (cytokines and chemokines) before, and after, treatment. Proteomic analysis will occur at Dalhousie's Proteomics and Mass Spectrometric Core Facility located in the Life Sciences Research Institute. This study may serve to help develop diagnostic protocols and methods of assessing response to treatments.

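### The RNA sub-study aspirate is taken from the centre of the lesion before pathology receives the specimen that supplies the diagnosis, depth and TIL reading

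*Combined protocol and SAP*

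**What the plan says.** The Research Plan section of the combined protocol and SAP sets out how the Day 15 specimen is handled. First, "using a 22G needle a fine needle aspiration biopsy will be performed", in which "the needle will be passed through the center of the lesion two times"; the stated purpose is RNA analysis. Next, "The remainder of the tissue will be sent to pathology for standard histological assessment".

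The same section lists what pathology must obtain from that tissue. It is examined "to confirm diagnoses, assess margin status (clear or involved) and depth of lesion invasion", and "The depth of lesion invasion will dictate the extent of subsequent surgical excisions and margin selection". The pathologist also reports the extent of TILs, by treatment and control.

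Under Outcome measure/study objectives, the first outcome concerns "study measures including tumor infiltrating lymphocytes (TILs) and circulating immunomodulators". RNA appears there under the sub-study outcomes, and Figure 2 labels the tissue sample "To be used in RNA analysis sub- study".

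The Research Plan has a separate provision for lesions too large for simple closure: 4 mm punch discs from representative areas. The processing instruction comes after that provision and makes no exception for it.

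**The concern.** One specimen serves three purposes: patient care, a leading study measure (TILs) and a sub-study assay. The plan gives first access to the sub-study assay, and at the centre of the lesion. If the needle removes or disrupts tissue where depth or infiltrate would have been read, two things are at risk. The patient's diagnostic information may be weakened, and this cannot be repaired because the lesion has already been removed or sampled. The TIL measure may also gain error or lose specimens in a trial that starts with 10 patients per arm.

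The plan contains no safeguard. It sets no minimum specimen size, does not let pathology decline or redirect the aspirate, does not ask for needle tracks to be recorded, and does not say how a disrupted specimen enters the TIL analysis. The Research Plan does consider whether the 0.1 ml injections disturb the lesion's architecture, but it does not ask the same question of the aspirate.

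**Working it through.** The plan gives no figure to reproduce. The point rests on the order of handling, so the text comes first and the arithmetic is only illustrative.

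**Order of access against rank of use**

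| Use of the specimen | Status in the plan | Access to tissue |
|---|---|---|
| RNA aspirate | Sub-study (Outcome measures; Figure 2) | First, two passes through the lesion centre |
| Diagnosis, margins, depth | Clinical; depth governs later surgery (Research Plan) | Remainder |
| TILs | Named in Aim 1 and in the first outcome | Remainder |

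No other section gives pathology earlier access.

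**Are punch discs aspirated?** The text points both ways.
- For: the processing instruction speaks of the biopsied specimen, directly follows the punch provision and makes no exception.
- Against: the needle goes through the centre of the lesion, which does not describe a disc cut from part of a large lesion. The Research Plan elsewhere ties the aspirate to excised samples, Figure 2 refers to tissue removed at excision, and the RNA outcome uses a comparator from the clear margins of the excisional biopsy.

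**Illustrative geometry**

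Inputs:
- D = 4 mm (punch disc, Research Plan) or D = 10 mm (assumed lesion).
- Track width d = 0.4 to 1.0 mm. This is assumed, because the plan gives only the gauge.
- Two separate, full-thickness tracks perpendicular to the face, with the full width removed. This is also assumed.

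Area share of two tracks = 2 × (d/D)². Share of the central diameter crossed by one track = d/D.

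| D | d | Area, two tracks | Diameter, one track |
|---|---|---|---|
| 4 mm | 0.4 mm | 2 × 0.1² = 2.0% | 10% |
| 4 mm | 0.7 mm | 2 × 0.175² = 6.1% | 17.5% |
| 4 mm | 1.0 mm | 2 × 0.25² = 12.5% | 25% |
| 10 mm | 0.4 mm | 2 × 0.04² = 0.3% | 4% |
| 10 mm | 0.7 mm | 2 × 0.07² = 1.0% | 7% |
| 10 mm | 1.0 mm | 2 × 0.1² = 2.0% | 10% |

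If the two tracks coincide, which is possible since both pass through the centre, the area shares halve.

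**Cost of a lost TIL reading.** One unreadable specimen is 1/10 = 10% of an arm at the 20-patient minimum and 1/30 = 3.3% at the 60-patient maximum. This is the cost per specimen if one is lost. The documents do not say how often that would happen.

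**The case against.** The strongest reply is that no harm is shown. Nothing in the documents indicates that two fine-needle passes would change a diagnosis, a depth or a TIL grade. Excision is the default, and in a lesion of about 10 mm the illustrated loss is 2% or less. The aspirate is done on tissue already removed, so it adds no procedure for the patient. This all stands, and it limits the point to a precaution about who has first access.

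A second reply is that RNA matters more than its sub-study label suggests. The Research Plan unmasks after the RNA, proteomic, metabolomic and pathology data have been analysed, and then stops or extends enrolment according to significance. RNA may therefore contribute to that decision, and losing RNA samples has a cost. This also stands and is carried into the fix. It does not justify placing RNA ahead of the patient's diagnosis.

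A reader might also infer more than the text supports:
- *Every specimen, including each punch disc, is needled.* The text is ambiguous, as shown above. Discs are also taken in the plural, so tissue could remain even if one were aspirated.
- *A single percentage of tissue is lost.* Any one figure depends on an assumed width, separate tracks and solid removal. Only the range is defensible.
- *The track is comparable in size to the depth being measured.* The Research Plan gives no unit for depth of invasion, and the width of a track and the depth of invasion are different dimensions.

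**Conclusion.** The point holds as one of priority. The plan explicitly lets a sub-study aspirate sample the centre of the lesion before pathology obtains the diagnosis, margins, depth and TILs, and it has no safeguard for small specimens. This is a stated rule, not a missing detail.

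A reader might infer that the comparison between arms is biased or that specimens will be spoiled. The documents support neither: the step is the same in both arms, and no rate of compromised specimens is given. What is at stake is diagnostic safety and the readability of TILs.

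The concern is greatest for small lesions and, if they are aspirated, for punch discs. It is slight for large excisions. The percentages shown are conditional on the assumed track width and geometry, and the conclusion does not depend on them. The change is worth making before enrolment because it is cheap and a compromised diagnostic specimen cannot be replaced.

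**What to change.** Rewrite the specimen-processing text in the Research Plan to state that:

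1. Tissue needed for diagnosis, margins, depth and TILs has priority.
2. The RNA aspirate is taken only from tissue that pathology releases, away from the area chosen for the depth reading.
3. A punch disc or other small specimen is not aspirated unless pathology releases it. This also settles whether discs fall within the step.
4. For each specimen, whether and where it was aspirated is recorded. Where nothing can be released, RNA is recorded as missing.

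The same paragraph should settle two neighbouring gaps. The RNA outcome takes comparator tissue from the clear margins without saying whether this precedes the margin report. The Research Plan also sends lesion biopsy samples straight to the research laboratory while sending the remainder to pathology.

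The cost is one paragraph and coordination with a pathology service that is already involved, with no extra patients or procedures. The downside is that some RNA samples will be later, smaller or missing. If RNA contributes to the decision to continue enrolment, the Research Plan's text on unmasking and extension should therefore state how missing RNA data are handled.

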#### Hypothesis:

*Hypothesis*: Pre-treatment with IL-2 in patients with highly suspicious pigmented lesions will reduce the incidence of metastatic melanoma compared to the PBS placebo group by initiating an adaptive immune response to native melanoma protein and peptide. *Major Aims*:

- 1) To conduct a pilot study to assess the number of patients needed to analyze in order to achieve a statistically significant differentiation between treatment and control outcomes in study measures including tumor infiltrating lymphocytes (TILs) and circulating immunomodulators.
- 2) To assess the efficacy of intralesional pre-treatment of IL-2 on highly suspicious lesions in generating an adaptive immune response and preventing melanoma metastasis.
- 3) Sub-study To assess if there a difference in specific immune modulators in patients receiving IL-2 pre-treatment compared to patients receiving a placebo.

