This study is a randomized, controlled, double-blind study. Patients with highly suspicious pigmented lesions will be randomly assigned by an algorithm to one of two groups: 1) treatment group patients will be treated intralesionally with IL-2 (Proleukin (Aldesleukin), Novartis Pharmaceuticals Canada Inc.) at a dose of 500,000 International Units (IU) (0.1ml) for 2 treatment cycles 1 week apart (Day 1 and Day 8) Figure 1; 2) control group patients will be treated intralesionally with sterilized sodium chloride (0.9%, m/v) (0.1ml) Figure 1. Randomization will be done at the pharmacy for each patient (generated by a Random Block algorithm). IL-2 (Proleukin) will be obtained from the Provincial Drug Distribution Program by the pharmacy, paid for by [name] research services account (please see budget attached). The pharmacy will prepare either IL-2 treatment (supplied as 1 x 0.8ml (4 million units) or injectable placebo (0.9% sodium chloride) supplied as 0.8ml). The syringes will be prepared by following aseptic technique in a biohazard hood. A 22-million unit vial of IL-2 will be reconstituted with 1.2ml of sterile water for injection and mixed gently. After drawing up 3.2ml of 5% dextrose in water and transferring to the IL-2 vial, the resulting concentration will be 5 million units/ml. 0.8ml of the IL-2 solution will then be drawn into a 3ml syringe. Expiry time of the reconstituted solutions is 48 hours at 4C. The pharmacy will assign a codified ID which will be provided along with the syringe with the patient name labeled as "Interleukin-2/Placebo" (thus blinding study to clinician and patient). As a pilot study, the principle of the design is to test the feasibility of proceeding to a larger and more expensive trial following the methodology and protocol proposed. As such there will be a minimum of 20 (10 treatment, 10 placebo) participants (up to a maximum of 60). It is estimated that statistical significance will be reached with 20 patients, however it is not reached after 20 patients, an additional 10 (5 treatment, 5 control) patients will be enrolled. If significance is still not reached after 30 patients, an additional 10 patients will be enrolled and so on up to a maximum of 60 patients. If after 60 patients, significance is not achieved then further recruitment under the current protocol would not be logical and therefore the methodology would need to be revised or study discontinued.

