All blood, urine, and lesion biopsy samples will be labeled with a codified number (will not contain any patient identifying information) and will be immediately transported to [name] laboratory (Sir Charles Tupper Medical Building, 11F11) at Dalhousie University for storage. Fine needle aspiration of excised samples will be assessed for tumor genetic and epigeneitic profile (Figure 2). Blood and urine will be assessed for proteomic and metabolomic profiles, respectively (Figure 2).

A database containing patient IDs and codified numbers will be restricted to the office of [name] (11th floor, VG). This is a locked office, and the data will only be accessible to the investigators named on this application. This database for will contain patient IDs, and info on disease status, treatment/control, follow up visits, and sample analysis – only info pertinent to the outcome measures. All sample data will be assessed using codified descriptors and will contain no patient ID info. Once the RNA, proteomic, metabolomic and pathology data has been analyzed, unmasking treatment and control groups will be conducted at the VG office of [name], by the named investigators. If the data reaches statistically significance, the study will not accept any more patients, if not, a further 10 patients will be incorporated – to a maximum of 60 patients. Any publications of study results will be completed devoid of any information that could be used to identify patients included in the study.

All study participants will receive biannual assessments for 5 years after the initial intervention to assess disease progression, or the development of new melanoma, to compare between both treatment and control groups. There is no standardize test or measurable biomarker to assess established or lasting immunity. This aspect of the study is identical to the patient assessment conducted as per standard of care for melanoma patients. Again, any publications of study results will be completed devoid of any information that could be used to identify patients included in the study.

	Interleukin 2 Treatment Group				
Interleukin-2 Treatment Group		Placebo Treatment Group			

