#### How will the data be analyzed:

All study practices and statistical methods are based on the International Conference on Harmonization (IHC) document "Statistical Principles for Clinical Trials." Data will be summarized by treatment group. Baseline characteristic, safety outputs and a total overall column will be included to summarize all subjects. For all baseline, demographic, safety and efficacy outputs data will be summarized by treatment group. In summary tables of continuous variables, the minimum and maximum statistics, the arithmetic mean and median, the 95% confidence interval, standard deviation, and standard error will be presented will to the same number of decimal places as the original data. In summary tables of categorical variables, counts and percentages will be used. The denominator for each percentage will be the number of subjects within the population treatment group unless otherwise specified. All hypothesis testing will be carried out at the 5% (2-sided) significance level unless otherwise specified. P-values will be rounded to three decimal places. P-values less than 0.001 will be reported as <0.001 in tables.

The treatment label for all tables, listings and figures will be:

Treatment	Label
2 treatment cycles of	IL-2
500,000 IU of IL-2 in 0.1	Treatment
mL	
0.1 mL of sterile saline	Placebo
(0.9% m/v)	
All Treatments	Total

Where that any of the statistical methods described herein prove unsuitable during analysis, more appropriate methods will be used. All changes in methodology will be documented in the clinical study report. Additional ad-hoc analyses may be conducted as deemed suitable.

Subject inclusion/exclusion criteria will be determined at baseline visit, and subjects who do not meet all criteria will not be entered into the study. Those subjects deemed eligible to participate will be allocated a 3-digit number at randomization prior to the initial treatment. If a subject is discontinued at any time after entering the study, the Investigator will ensure this does not affect the patient's standard of care. At the patients request all unused biological samples (blood, urine, and core biopsies) will be immediately destroyed. The reasons for withdrawal will be recorded on the CRF and will be included in the final report. Failure to complete both (2) treatment cycles will result in patient removal from the trial.

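### The enrolment rule does not say which measure decides, or whether one significant measure is enough, so a chance cytokine result could close recruitment with no TIL difference

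*Combined protocol and SAP*

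**What the plan says.** The enrolment rule appears twice in the Research Plan.

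- The design paragraph starts with "a minimum of 20 (10 treatment, 10 placebo) participants (up to a maximum of 60"). If significance is not reached at 20, "an additional 10 (5 treatment, 5 control) patients will be enrolled", and so on up to 60. It does not say significance of what.
- The paragraph on the database and unmasking says "Once the RNA, proteomic, metabolomic and pathology data has been analyzed, unmasking treatment and control groups will be conducted", and then "If the data reaches statistically significance, the study will not accept any more patients, if not, a further 10 patients will be incorporated".

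Two other places bear on which measures count.

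- Major Aim 1, under Hypothesis, seeks the number of patients needed for a "statistically significant differentiation between treatment and control outcomes in study measures including tumor infiltrating lymphocytes (TILs) and circulating immunomodulators". The first outcome under Outcome measure/study objectives repeats the list: "study measures including tumor infiltrating lymphocytes (TILs) and circulating immunomodulators". Neither place calls any measure primary.
- Under the proteomic outcome, serum is used to assess "protein expression, including circulating immunomodulators (cytokines and chemokines) before, and after, treatment". The immunomodulators are thus several analytes, and their number is not given.

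The RNA, proteomic and metabolomic assessments are headed as sub-study outcomes, and Figure 2 shows them as sub-study procedures. On error control, How will the data be analyzed says only: "All hypothesis testing will be carried out at the 5% (2-sided) significance level unless otherwise specified". No multiplicity adjustment is specified.

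**The concern.** A rule that stops recruitment on significance needs three things: the measure, the test, and what to do when measures disagree. The plan gives the level of each test but not the measure or the way results combine. A reader applying it at 20 patients, with one cytokine at p = 0.03 and TILs showing no difference, could defensibly stop or continue.

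This matters for two reasons. First, the rule fixes the trial's own sample size, and Aim 1 makes the number of patients needed for significance a main output. That number cannot be interpreted unless one knows which measure produced it. Second, the rule is applied by the investigators after unmasking, so the deciding measure could be chosen with the group labels known.

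The Lay Summary presents the TIL response as the sign of an effective immune response and builds the pre-treatment hypothesis on it. A stop on a laboratory marker alone would leave that comparison at its smallest size. The problem exists at a single look, so it is distinct from the repeated looks, which add to it.

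**Working it through.** **Is there a figure to reproduce?** The plan expects significance at 20 patients but gives no endpoint, effect size, standard deviation or power, so the 20 cannot be reproduced. For scale, a two-sample t-test with 10 per arm at two-sided 5% needs a standardized difference of about 1.32 for 80% power. The plan does not say for which measure such a difference is expected.

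**Inputs from the plan**
- Level: 0.05 two-sided per test (How will the data be analyzed).
- First look: 20 patients, 10 per arm. Later looks: 30, 40, 50 and 60, so five in all (Research Plan).

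**Assumptions**
- Number of measures m: 2, 5, 10 or 20. The plan gives no count; it names two kinds of measure, one of them plural.
- Any one significant measure stops recruitment. The plan leaves this undefined.
- No true difference on any measure.

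**Step 1. First look, independent measures.** False-stop chance = 1 − 0.95^m.
- m = 2: 1 − 0.9025 = 9.75%
- m = 5: 1 − 0.7738 = 22.6%
- m = 10: 1 − 0.5987 = 40.1%
- m = 20: 1 − 0.3585 = 64.2%

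**Step 2. First look, correlated measures.** Simulated two-sample t-tests, 10 per arm, common pairwise correlation, 200,000 trials per cell:

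| m | independent (formula) | correlation 0.5 | correlation 0.8 |
|---|---|---|---|
| 2 | 9.75% | 9.1% | 7.9% |
| 5 | 22.6% | 18.6% | 13.2% |
| 10 | 40.1% | 29.7% | 18.1% |
| 20 | 64.2% | 43.5% | 23.7% |

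Every cell exceeds 5%.

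**Step 3. A stop without a TIL difference.** With TIL plus k other independent null measures, the chance that TIL is not significant but another measure is, at the first look, is 0.95 × (1 − 0.95^k).
- k = 4: 0.95 × 0.1855 = 17.6%
- k = 10: 0.95 × 0.4013 = 38.1%

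**Step 4. What remains once one endpoint decides.** At the first look the chance returns to 5%. Over five unadjusted looks (10, 15, 20, 25 and 30 per arm; 400,000 simulated trials) the cumulative chance for one null measure is 4.9%, 7.7%, 9.8%, 11.5% and 13.0%. A constant level that holds 5% overall across these looks is about 0.018 two-sided per look (|z| about 2.37).

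**The case against.** The strongest reply is that the plan never says one significant measure suffices. That is correct. A reader might infer from the stopping sentence that any single cytokine, metabolite or transcript below 0.05 meets the rule. The wording refers only to the data as a whole and leaves any or all open. The defect is an undefined rule, and the percentages above hold only under its permissive reading.

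A second reply is that the RNA, proteomic and metabolomic results are labelled sub-study outcomes, and that the sentence listing them fixes when unmasking occurs, not what decides. This also has force, and it weakens the case for a metabolite or transcript as trigger. It does not settle the matter, because those results are listed immediately before the stop decision and nothing excludes them. It does not help at all for cytokines: circulating immunomodulators are named in Aim 1 and appear again in the proteomic sub-study.

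Third, three consequences that a reader might draw go too far.
- The plan does not claim 5% for the enrolment decision; it sets 5% per test.
- The TIL question would not go unanswered, since the pathologist reports TILs for the biopsied specimens. The answer would be less precise.
- The plan does not say that 20 would be carried into the larger trial; that is an inference from Aim 1 and the pilot purpose.

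Finally, this is a pilot, and a multiplicity-adjusted pair (TIL plus one prespecified immunomodulator) would also work. Both points are fair. But this pilot sets its own size by hypothesis tests, and a pair would still have to be named.

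**Conclusion.** The concern holds as a gap in the decision rule. No section names the deciding measure, says whether any or all must be significant, or adjusts for several measures, so a stop on one chance cytokine without a TIL difference is permitted, though not prescribed.

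Under the any-one reading, the first-look false-stop chance exceeds 5% whenever more than one measure counts. It is roughly 8% to 10% for two measures and 24% to 64% for twenty, depending on correlation between 0.8 and none. The direction is certain under that reading. The size is not, because it depends on an assumed number of measures and an assumed correlation. Because the rule governs sample size and is applied after unmasking, it should be settled before the first unmasking.

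**What to change.** Make the same change in Major Aim 1, in both statements of the enrolment rule in the Research Plan, and in Outcome measure/study objectives:

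1. Name one deciding measure: the Day 15 TIL comparison of IL-2 versus placebo. Fix its scoring scale and its test before any unmasking. The plan now says only that the pathologist reports the extent of TILs, so naming TILs without a scale would leave the rule undefined.
2. State that circulating immunomodulators and the RNA, proteomic and metabolomic sub-study results play no part in the enrolment decision. Report them as secondary or exploratory, with estimates, intervals and false-discovery-rate control within each platform.
3. State that this removes only the multiple-measure part of the error. The per-look level must be adjusted separately for the five looks; a constant level of about 0.018 is one option.

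The cost is wording: the pathologist already reports TILs, so no new samples or visits are needed. The downsides are that a circulating marker alone can no longer close recruitment, and that Aim 1, which now places immunomodulators beside TILs, must be reworded.

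### Patients are read and unmasked in successive sets, but no model or set term is named; if readings differ between sets, the pooled standard error is too large beyond 20 patients

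*Combined protocol and SAP*

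**What the plan says.** The Research Plan sets the size in steps: "there will be a minimum of 20 (10 treatment, 10 placebo) participants (up to a maximum of 60"). If the first test fails, "an additional 10 (5 treatment, 5 control) patients will be enrolled". After that, "If significance is still not reached after 30 patients, an additional 10 patients will be enrolled and so on", to the ceiling of 60. The 5/5 split is written out only for the set that takes enrolment from 20 to 30; the later tens appear to follow the same pattern.

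Allocation is patient by patient: "Randomization will be done at the pharmacy for each patient (generated by a Random Block algorithm"). No block size is given.

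On the order of events, the same section says: "Once the RNA, proteomic, metabolomic and pathology data has been analyzed, unmasking treatment and control groups will be conducted". The continuation decision follows: "If the data reaches statistically significance, the study will not accept any more patients, if not, a further 10 patients will be incorporated".

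The section on how the data will be analysed says: "All hypothesis testing will be carried out at the 5% (2-sided) significance level unless otherwise specified". It describes summary tables by treatment group. It names no test, regression model, covariate, recruitment-set term or assay-run term, and it does not require a patient's Day 1 and Day 15 samples to be run together.

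**The concern.** The next ten patients are recruited only after the earlier patients' RNA, proteomic, metabolomic and pathology results have been read and unmasked. A trial that goes to 60 therefore produces its readings in up to five rounds, unless stored samples from earlier rounds are re-assayed. PCR and mass-spectrometry readings can shift between rounds.

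With arms balanced inside each set, such a shift does not bias the treatment difference. A pooled comparison that ignores set still counts it as random error. Each test after the first then has a standard error larger than the true one. These same tests decide whether recruitment continues, so the cost would be some lost power, intervals that are too wide, and a few extra patients.

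**Working it through.** **The plan's own figure.** The plan expects significance at 20 patients but gives no effect size, SD or power, so that number cannot be reproduced. Inverting the two-means formula at 10 per arm, two-sided 5%, 80% power: d = (1.960 + 0.842) × √(2/10) = 1.25 SD (1.32 SD with the t distribution).

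**Inputs from the documents.** Sets of 20, 10, 10, 10 and 10; arms balanced within set; tests at 20, 30, 40, 50 and 60; each at 5% two-sided; recruitment stops at the first significant result.

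**Assumptions.** One continuous endpoint with within-set SD 1. A share ρ of total variance lies between sets, so the between-set variance is σ_b² = ρ/(1 − ρ). I take ρ = 0.1, 0.2 and 0.4. The effect is 0.8 within-set SD.

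**Standard error at N = 60.** Set effects cancel from the treatment difference, so its true standard error is √(4/60) = 0.258. Without a set term, the expected residual variance is

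1 + σ_b² × (N − Σn_k²/N)/(N − 2).

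Here Σn_k² = 400 + 4 × 100 = 800, so N − Σn_k²/N = 60 − 13.33 = 46.67, and 46.67/58 = 0.805.

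- ρ = 0.1: σ_b² = 0.111; √(1 + 0.089) = 1.044
- ρ = 0.2: σ_b² = 0.250; √(1 + 0.201) = 1.096
- ρ = 0.4: σ_b² = 0.667; √(1 + 0.536) = 1.24

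Simulated mean standard errors are 0.268, 0.281 and 0.317 without the term, against 0.257 with it. The ratios are 1.04, 1.09 and 1.23, in line with the formula.

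**At N = 20.** N − Σn_k²/N = 20 − 400/20 = 0. There is one set, the ratio is exactly 1, and the term has nothing to act on.

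**The five-look rule, simulated (t-test v set-plus-treatment linear model).**

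| ρ (assumed) | Cumulative power, 0.8 SD: without v with | Mean enrolment: without v with | Overall type I error: without v with |
|---|---|---|---|
| 0.1 | 88% v 89–90% | 34.8 v 34.3 | about 12% v 13% |
| 0.2 | 86–87% v 89–90% | 35.4 v 34.4 | about 11% v 13% |
| 0.4 | 80–81% v 89–90% | 36.8 v 34.3 | about 9% v 13% |

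Independent runs put the rise in mean enrolment at 0.4–0.5, 1 and 2.4–2.5 patients. For an effect near 1.3 SD, which gives about 80% power at 20 patients, the difference is under one patient.

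**Cost of the term.** Residual degrees of freedom at N = 60 fall from 60 − 2 = 58 to 60 − 1 − 5 = 54. With no between-set variance, power of a single test at 60 is about 86% either way.

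**Repeated testing by itself.** With no between-set variance, the cumulative type I error over the five looks is 5.0%, 7.7%, 9.7%, 11.4% and 12.7%. A constant nominal level of about 0.018 (|z| about 2.37) brings it to 5%.

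**The case against.** The strongest reply has four parts.

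- **The batch premise is inferred.** The documents describe no assay runs and give no batch variance. A recruitment set is not necessarily one run. This stands, and it is why the sizes are shown as a range. At a 10% share the power loss is only 1 to 2 points.
- **Some measures are partly protected.** Tumour infiltrating lymphocytes are reported by a pathologist from standard histology and are not described as a batch assay. Immunomodulators are compared before and after treatment, and RNA with the patient's own unaffected tissue. Additive shifts cancel in such comparisons, but only if the patient's samples share a run, which the plan does not require. The lymphocyte reading has no pre-treatment value, so it lacks that protection, though its drift between sets may be small.
- **No model is specified, so every term is missing.** Correct. A reader might infer that a pooled model was chosen and set was left out of it. The documents do not support that. The gap is that no model is named, and a set term belongs in it when it is written.
- **Balance may not survive.** Block size is unstated, and patients who miss a treatment cycle are removed, so analysed sets need not be exactly 5/5. This weakens the exact formula but does not argue against the term.

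A reader might also infer that the trial's test is too conservative. That holds for one test taken alone: at 60 patients without the term, null rejection falls to about 4%, 3% and 2%. The plan does not make one test. It tests up to five times at 5% and stops on success, so the overall error stays well above 5% at every share examined.

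**Conclusion.** The point holds as a minor refinement. The step-wise design is explicit, arms are intended to balance within sets, and the analysis section provides nothing to separate set-to-set variation from error. If that variation exists, pooled standard errors after the first look are too large. The loss of cumulative power at 0.8 SD runs from 1–2 points at a 10% share to about 9 points at 40%, and average extra enrolment is at most about 2.5 patients. If the trial stops at 20, as the plan expects, there is no effect.

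These figures rest on the assumed between-set shares, the assumed effect, a single continuous endpoint, balanced sets, and a full batch shift applied to each reading. For change scores from samples run together, the benefit would be smaller.

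The documents do not support a claim of large over-enrolment. Nor would a set term correct the repeated testing: it moves the overall error slightly up, to about 13%. The repeated testing is the larger defect and needs its own remedy.

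**What to change.** - When the primary model is written, include recruitment set (first 20, then each ten) as a fixed factor in every pooled between-arm analysis once enrolment exceeds 20.
- Adopt it together with a pre-specified sequential boundary, for example a nominal level of about 0.018 at each of the five looks. The power figures above use the unadjusted 5% looks and would need recalculating under the boundary.
- Require each patient's Day 1 and Day 15 blood and urine samples to be assayed in the same run, and record the run.

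The set term costs a few lines of SAP text and up to four degrees of freedom at 60 patients, none at 20, with essentially no power lost if sets do not differ. Same-run assay is a laboratory scheduling instruction. The boundary is a separate change: it lowers the chance of stopping at each look, which is the price of holding the stated 5%.
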